3.3 Known Potential Risks to All Anticoagulation Clinic Patients who Undergo Chart Review

Chart review of all anticoagulation clinic patients who are documented in the electronic health record as using CAT without PPI gastroprotection at study initiation will be completed to provide information about the number of patients who may require medication optimization in the future clinic-wide trial and about the use of the evidence-based medication optimization strategies in usual practice to assess feasibility of completing the future clinic-wide trial. Anticipated risks to patients who are not randomized to receive a QI strategy and solely undergo chart review are minimal.

1. **Breach of Data Confidentiality.** It is possible that the identity of the participant or protected health information (PHI) could be unintentionally revealed to persons outside of the research team. As this study does not deal with sensitive or stigmatized behavior (i.e., illicit drug use), a potential data breach is anticipated to cause minimal harm to the participant if it were to occur.

3.4 Known Potential Risks to Clinicians and Staff (Group 1 and Group 2)

1. **Potential Psychological Discomfort due to Subject Content.** The clinician messages and assessment will deal with the topic of clinical care practices, including opportunities for clinical care improvement. This could cause clinicians to be upset or concerned. All efforts will be made to discuss these topics in a careful and thoughtful manner.
2. **Inconvenience.** Clinician participants may feel inconvenienced by the attempts to reach them or the time it takes to engage with communications from anticoagulation clinic staff or in the clinician assessment.
3. **Breach of Data Confidentiality.** It is possible that the identity of the participant could be unintentionally revealed to persons outside of the research team. However, no PHI will be sought from clinicians. As this study does not deal with sensitive or stigmatized behavior (i.e., illicit drug use), a potential data breach is anticipated to cause minimal harm to the participant if it were to occur.

3.5 Known Potential Benefits to Randomized Patients (Group 1)

Potential benefits associated with study participation include:

1. **Increased knowledge and understanding of personal risk** for GI bleeding, which will be discussed in the patient activation guide and during research interviews.
2. **Increased sense of self-efficacy** to discuss risk status and medication optimization with their clinicians.
3. **Reduced risk of upper GI bleeding events** if patients have medication optimization as a result of participation.

4. **Self-Satisfaction** – participants may derive a sense of personal satisfaction and purpose from contributing new knowledge to help advance science and medicine.

3.6 Known Potential Benefits to Randomized Patients (Group 2)

Potential benefits associated with study participation include:

1. **Increased knowledge and understanding of personal risk** for GI bleeding, which will be discussed in the patient activation guide.
2. **Increased sense of self-efficacy** to discuss risk status and medication optimization with their clinicians.
3. **Reduced risk of upper GI bleeding events** if patients have medication optimization as a result of participation.

3.7 Known Potential Benefits to All Anticoagulation Clinic Patients who Undergo Chart Review

Potential benefits for all patients who receive care from the anticoagulation clinic service who are not randomized to receive one of the QI strategies but are identified as being at high-risk for upper GI bleeding through a workbench report in MiChart at baseline and undergo chart review include:

1. **Increased knowledge and understanding of the prevalence of CAT use without PPI gastroprotection** among patients cared for by the anticoagulation clinic will help gain clinic leadership buy-in to allocate resources to lower bleeding risk and improve patient safety through wide-scale implementation of the QI strategies being tested.

3.8 Known Potential Benefits to Clinicians and Staff (Group 1 and Group 2)

1. **Increased knowledge** of risk factors for upper gastrointestinal bleeding and of evidence-based practices to reduce the risk.
2. **Self-Satisfaction** – clinicians and anticoagulation clinic staff may derive a sense of satisfaction and purpose from working to prevent bleeding and adverse events related to warfarin use in their patient population.

3.9 Assessment of Potential Risks and Benefits

The risks to patients, clinicians and staff are all minimal and justified by the value of the potential benefits and knowledge gained. Risks of confidentiality breach will be mitigated by separation of personal identifiers (consent forms, enrollment forms) from data source documents. All data

source documents and any personally identifying information for trial participants will be stored on a secure drive or in a locked file cabinet and will be accessible only to the study team.

4 OBJECTIVES AND ENDPOINTS

4.1 Objectives and Endpoints (Group 1)

OBJECTIVES	ENDPOINTS
Primary	
To explore the feasibility of patient participation in a one-time assessment of medication use following delivery of the QI strategies.	Proportion of patient participants who are able to be contacted by phone and are willing to participate in and fully complete patient assessment #1, related mainly to medication use (week 5 interview).
Secondary	
To explore the feasibility of delivering QI strategy components as intended.	Proportion of participants who received all implementation components to which they were randomized in the appropriate time frame.
Exploratory	
To explore additional aspects of the feasibility of recruitment.	Proportion of randomized patients able to be reached by phone after three attempts for patient assessment #1 at week 5. Average number of phone call attempts to reach each patient for patient assessment #1 at week 5. The number of anticoagulation clinic patients who meet eligibility criteria for the AEGIS trial on the first day of the pilot study according to the EHR workbench report.
To explore changes in the proportion of eligible patients during the study duration.	The proportion of all patients in the anticoagulation clinic who meet eligibility criteria for the study, regardless of whether they are included, who discontinued warfarin or were otherwise closed to the anticoagulation service during the study period. The proportion of patients who were randomized who discontinued warfarin or were closed to the anticoagulation clinic service during the participants' study duration.

OBJECTIVES	ENDPOINTS
To explore the accuracy of the electronic health record's medication list for ascertaining inclusion criteria	
The proportion of randomized patients who, retrospectively, report that they had been using antiplatelet therapy at baseline during patient assessment #1 at week 5.
 
The proportion of randomized patients who, retrospectively, report that they had been using PPI at baseline during patient assessment #1 at week 5.
 
The proportion of randomized patients who met inclusion criteria based on retrospective medication use in patient assessment #1 at week 5.

To explore the accuracy of the electronic health record's medication list for ascertaining medication changes	
The accuracy, positive predictive value, and negative predictive value of the electronic health record for use of antiplatelet therapy, and for use of PPIs at the time of assessment #3.
 
The accuracy, positive predictive value, and negative predictive value of the electronic health record for "medication optimization" at the time of assessment #3. A patient will be considered to have had medication optimization if they are either no longer using combination antithrombotic therapy or are using a PPI.

To explore the feasibility of complete collection of study data	
The proportion of patients with complete data entry in RedCAP database at study completion
 
Average duration of interviews on medication use/adherence during patient assessment #3 at week 15-17.

To explore the feasibility of delivering the clinician-level QI strategies	
Proportion of patients whose clinician was sent the clinician-level strategy by the anticoagulation clinic staff in the prescribed time period per the clinic protocol. We will also separately calculate this endpoint for the two levels of the clinician QI strategy.

To explore the feasibility of delivering the patient activation tool	
The proportion of patients randomized to receive the activation guide who were sent the guide in the prescribed period of time, as determined by chart review.
 
The proportion of patients randomized to receive the guide who recalled receiving the guide during patient assessment #1 at week 5.
 
The proportion of patients randomized to receive the guide who recalled reviewing the guide in patient assessment #1 at week 5.

OBJECTIVES	ENDPOINTS

To explore the feasibility of prompting patient-clinician communication about medication optimization
	
The number of days after delivery of the clinician-facing QI strategy at which the patient and the target clinician (or their healthcare team) had communication (either by phone, in person visit, or portal message) about medication optimization, based on chart review. This will be calculated overall and separately for each QI strategy.
 
The proportion of patients who had a communication about medication optimization with their clinicians based on patient recall at week 5 (patient assessment #1) and at week 9-12 (patient assessment #3). This will be calculated overall and separately for each QI strategy.
 
For patients who had a communication with their clinician about medication optimization, the proportion in whom initial contact was made by the clinician vs. by the patient, according to chart review. This will be calculated overall and separately for each of the QI strategies. This will be assessed based on week 5 call.
 
For patients who had a communication with their clinician about medication optimization, the proportion in whom initial contact was made by the clinician vs. by the patient, according to patient recall. This will be calculated overall separately for each QI strategy.
 
For patients who contacted a clinician about medication optimization, the specialty of the clinician and whether the clinician who was sent the clinician notification was the target clinician. This will be determined separately based on chart review and patient recall.
 
For patients who had communication with their clinician documented in the electronic health record, whether this occurred by phone, portal, or in-person/telehealth visit based on chart review.

To explore process measures associated with clinician notification
	
For clinicians randomized to clinician notification:
 
Number of days taken for clinicians to send a response message to anticoagulation staff after first receiving the clinician QI strategy.
 
Proportion of clinicians who documented their plan-of-care for the patient in the response message to the anticoagulation staff.
 
The number of clinicians who appropriately documented changes in antiplatelet drugs or PPI in the EHR medication list.

OBJECTIVES	ENDPOINTS
To explore process outcomes associated with the clinician notification + nurse facilitation implementation strategy	
For patients randomized to clinician notification + nurse facilitation:
 
Number of days taken for clinicians to send a response message to anticoagulation staff after first receiving the clinician notification.
 
Proportion of clinicians who documented their plan-of-care for the patient in the response message to the anticoagulation staff.
 
Proportion of patients randomized to clinician notification + nurse facilitation for whom the anticoagulation nurse provided patient education.
 
Proportion of patients randomized to clinician notification + nurse facilitation for whom the anticoagulation nurse pended the PPI order.

To explore aspects of effectiveness of the implementation strategies.	
For anticoagulation clinic patients who meet inclusion criteria but are not randomized to a QI strategy in the pilot trial, whether or not they initiate PPI or discontinue antiplatelet therapy over the study period, as determined using electronic health record data, which will provide data on use of the evidence-based practices in usual care.
 
For randomized patients, initiation of either a PPI or discontinuation of all antiplatelet therapy at week 5 (patient assessment #1), and at week 15-17 (patient assessment #3), as determined by patient interview.
 
For randomized patients, the level of adherence to the recommended medication change (either PPI initiation or antiplatelet discontinuation) at week 15-17 measured using the Wilson questionnaire, as determined by patient assessment #3.
 
Documentation of a recommendation by one of the patient's Michigan Medicine clinicians to discontinue antiplatelet therapy or initiate a PPI as indicated by a clinical documentation or by a change in the EHR medication list, ascertained by EHR review.

To explore the appropriateness of antiplatelet therapy used by patients at the time of study randomization.	The clinical appropriateness of antiplatelet therapy at the time of study initiation, classified as either (probably guideline concordant, probably not guideline concordant, or uncertain), based on detailed chart review and in reference to practice recommendations (Appendix 1).

OBJECTIVES	ENDPOINTS
To explore the appropriateness of medication changes in antiplatelet therapy during the trial.	For patients who either stopped antiplatelet therapy or initiated a PPI during the trial, to explore the appropriateness of antiplatelet management according to patient-reported use in patient assessment #3 at week 15-17. The clinical appropriateness of antiplatelet management will be determined according to pre-specified criteria (probably guideline concordant, probably not concordant, uncertain). See appendix 1 for criteria.

Additional objectives to be explored in qualitative interviews with patients, clinicians, and anticoagulation clinic staff:

- Acceptability of the implementation strategy components
- Perceptions of the implementation strategies
- Barriers to successful implementation

Please see associated interview guides. The interview guides used to complete patient, clinician, and anticoagulation clinic staff assessments will be iteratively revised throughout the pilot study, allowing initial findings from assessments to inform subsequent assessments and ensuring capture of all relevant information necessary for effective planning of the future clinic-wide quality improvement trial.

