1 PROTOCOL SUMMARY

1.1 Synopsis

Title:	Anticoagulation with Enhanced Gastrointestinal Safety (AEGIS): A pilot quality improvement trial to evaluate clinician- and patient-facing strategies to reduce upper gastrointestinal bleeding risk in patients on combination antithrombotic therapy
Grant Number:	K23 DK118179
Background	
Patients who use an anticoagulant together with an antiplatelet drug (combination antithrombotic therapy, or CAT) are at increased risk for serious bleeding, which most commonly occurs in the gastrointestinal tract. For patients on CAT, there are two evidence-based medication optimization strategies to reduce upper gastrointestinal (GI) bleeding risk. Many of these patients may safely discontinue the antiplatelet drug. For patients who must continue the antiplatelet drug, proton pump inhibitors (PPIs) effectively reduce upper GI bleeding risk. Both of these strategies are underused. The aim of this trial is to evaluate the feasibility of conducting a future large-scale randomized quality improvement trial of quality improvement (QI) implementation strategies to increase medication optimization for patients on CAT at high risk for upper GI bleeding.

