8 END-OF-INTERVENTION/END-OF-STUDY

8.1 Discontinuation of Intervention

8.1.1 Group 1

Use of the implementation strategies will be discontinued for patients who discontinue warfarin therapy or are closed to the anticoagulation clinic service during the first 5 weeks of study participation. Such patients will not be included in the analyses, and will not receive patient assessment #1, #2, or #3.

For patients who discontinue warfarin or are closed to the anticoagulation clinic between week 5 and the end of the study, they will be contacted for patient assessment #1 and #2 but not #3. They will be included in the analysis of the primary and secondary outcomes, as well as the

exploratory outcomes, except those related to patient assessment #3 (e.g., medication adherence, appropriateness of antiplatelet therapy at week 15-17).

8.1.2 Group 2

Use of the implementation strategies will be discontinued for patients who discontinue warfarin therapy or are closed to the anticoagulation clinic service during the first 3-5 weeks of study participation. Such patients will not be included in any analyses.

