14 APPENDICES

14.1 Appendix 1. Criteria for determining appropriateness of antiplatelet therapy.-

Recommended duration of anti-platelet therapy for patients using anticoagulation, by indication.
Clinicians should use their judgment in applying these recommendations to patients depending on the specific clinical scenario.

Indication for antiplatelet drug	Recommended management of antiplatelet drug	Notes	Ref.
Primary prevention of coronary artery disease			
Primary prevention	Stop antiplatelet drug		¹
Treatment of coronary artery disease with atrial fibrillation (AF)			
PCI ≤ 6 months ago	Continue antiplatelet drug	Clopidogrel preferred	¹

PCI for stable CAD	PCI 6-12 months ago	Continue antiplatelet drug	Consider switch to aspirin 81mg	
	PCI >12 months ago	Stop antiplatelet drug		
CABG for stable CAD	CABG ≤12 months ago	Continue aspirin 81mg		
	CABG >12 months ago	Stop aspirin		
Acute Coronary Syndrome (ACS) +/- PCI	ACS +/- PCI ≤12 months ago	Continue antiplatelet drug	Clopidogrel preferred	
	ACS +/- PCI >12 months ago	Stop antiplatelet drug		

Treatment of coronary artery disease with venous thromboembolism (VTE)

PCI for stable CAD	PCI <3 months ago	Continue antiplatelet	Clopidogrel preferred	1
	PCI 3-6 months ago	Continue antiplatelet drug	-Clopidogrel preferred -Consider stopping anticoagulant if reversibly provoking risk factors	
	PCI >6 months ago	Continue antiplatelet drug	-Consider switch to aspirin 81mg -Consider stopping anticoagulant if reversibly provoking risk factors	
	PCI >12 months ago	Stop antiplatelet drug	-Consider stopping anticoagulant if reversibly provoking risk factors	
CABG for stable CAD	CABG ≤12 months ago	Continue aspirin 81mg		
	CABG >12 months ago	Stop aspirin		
Acute coronary	ACS +/- PCI <3 months ago	Continue antiplatelet drug	Clopidogrel preferred	

syndrome (ACS) +/- PCI	ACS +/- PCI 3-12 months ago	Continue antiplatelet drug	-Consider switch to aspirin 81mg -Consider stopping anticoagulant if reversibly provoking risk factors	
	ACS +/- PCI >12 months ago	Stop antiplatelet drug	-Consider stopping anticoagulant if reversibly provoking risk factors	
Cerebrovascular disease				
History of TIA, CVA, or CEA		Stop antiplatelet drug		1
Carotid stent ≤ 3 months ago		Continue antiplatelet drug	Clopidogrel preferred	
Carotid stent > 3 months ago		Stop antiplatelet drug		
Peripheral arterial disease				
Endovascular intervention or surgical repair ≤ 1-3 months ago		Continue antiplatelet drug	Clopidogrel preferred	1

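### Section 8.1.1 drops randomized patients who stop warfarin, against 11.2.1 and at the expense of the uptake results; the EHR-accuracy definition of optimization also includes a state that this rule makes unobservable

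*Combined protocol and SAP*

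**What the plan says.** **Exclusion rule (8.1.1, Group 1).** For patients who stop warfarin or are closed to the clinic in the first 5 weeks: "Such patients will not be included in the analyses, and will not receive patient assessment #1, #2, or #3". For those who do so between week 5 and the end of the study: "they will be contacted for patient assessment #1 and #2 but not #3". The later group stays in the primary, secondary and "exploratory outcomes, except those related to patient assessment #3". Section 5.4.1 places the end of the study for patients after week 28; assessment #3 is at weeks 15-17 (9.2.2).

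**Analysis set (11.2.1).** The primary and secondary analyses take in everyone randomized. Sections 11.5.1 and 11.6.1 likewise use randomized patients as the denominator.

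**Two definitions of a successful medication change (4.1).** The EHR-accuracy row concerns the accuracy, positive predictive value and "negative predictive value of the electronic health record for 'medication optimization' at the time of assessment #3". It classes a patient as optimized "if they are either no longer using combination antithrombotic therapy or are using a PPI". The effectiveness row, which is the uptake endpoint for randomized patients, counts "initiation of either a PPI or discontinuation of all antiplatelet therapy at week 5" and again at weeks 15-17, by patient interview. Section 9.6.2 also speaks of two qualifying changes.

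**Related text.** The synopsis defines combination therapy as an anticoagulant plus an antiplatelet, so stopping either drug ends it. Appendix 1 has a note in some venous thromboembolism rows: "Consider stopping anticoagulant if reversibly provoking risk factors". Section 4.1 has a separate exploratory endpoint for the proportion of randomized patients who stopped warfarin or were closed to the clinic.

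**The concern.** Leaving the analysis under 8.1.1 depends on an event after randomization. This has four consequences.

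- The early rule and 11.2.1 give different denominators for the primary and secondary endpoints.
- A patient who starts a PPI in week 2 and stops warfarin in week 4 meets the uptake endpoint but disappears from the result.
- A patient who completes assessment #3 in week 16 and stops warfarin in week 20 falls, as worded, under the later exclusion, although the data are in hand.
- The EHR-accuracy definition contains a state, combination therapy ended by stopping the anticoagulant, that patients cannot be observed in under 8.1.1.

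The pilot is meant to inform a larger trial of similar design (5.2). An exclusion rule and an outcome definition that do not fit each other could be carried into it.

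**Working it through.** The plan states no figure that depends on this rule, so there is none to reproduce. The check is a comparison of text, followed by illustrations.

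**1. Early stops against 11.2.1.** Section 8.1.1 takes stops in weeks 0-5 out of the analyses without qualification; 11.2.1 keeps them in. Both cannot hold. The later rule does not conflict with 11.2.1, because it touches only exploratory outcomes.

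**2. What this can do to the primary endpoint.** Early stoppers are never called for assessment #1, so in an all-randomized denominator they count as non-completers unless the plan says otherwise. Section 11.5.1 accepts the hypothesis if the normal-approximation 95% interval excludes 0.66. The lower limit is p - 1.96 x sqrt(p(1-p)/n). The number of early stops is assumed; completion is set near the 80% of 11.1.1.

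| Early stops | Stoppers removed | Stoppers kept |
|---|---|---|
| 1 of 51 | 40/50 = 80.0%, lower limit 68.9% | 40/51 = 78.4%, lower limit 67.1% |
| 3 of 51 | 38/48 = 79.2%, lower limit 67.7% | 38/51 = 74.5%, lower limit 62.5% |

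With one early stop the conclusion is the same either way. With three it depends on which section is followed.

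**3. Uptake under the effectiveness definition.** Let N = 51 (upper target, 6.1.1), k = patients removed after stopping warfarin, m = those among the k who started a PPI or stopped the antiplatelet, and 30% = assumed uptake in the N - k who remain. Then:

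uptake in all randomized = (0.30 x (N - k) + m) / N

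- k = 3, m = 0: 0.30 x 48 / 51 = 14.4/51 = 28.2%
- k = 5, m = 0: 0.30 x 46 / 51 = 13.8/51 = 27.1%
- k = 3, m = 1: 15.4/51 = 30.2%
- k = 5, m = 2: 15.8/51 = 31.0%

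The figure falls when stoppers make qualifying changes less often than other patients and rises when they make them more often. The documents give neither k nor m.

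**4. Chart data exist for these patients.** Section 9.6.1 plans chart review, including medication changes, for each participating patient. Section 8.3.1 keeps patients who cannot be reached by phone in the chart-based exploratory outcomes. Section 9.6.2 counts qualifying changes among all patients eligible at study initiation and states no exclusion for warfarin stops. As written, randomized and non-randomized uptake would rest on differently selected groups.

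**5. The optimization definition.** Combination therapy ends if either drug stops. Stopping the antiplatelet counts in both 4.1 definitions. Stopping the anticoagulant without replacement counts only in the EHR-accuracy row, and those patients have no assessment #3. The reference standard is self-report (11.7.1), and the listed content of assessment #3 covers antiplatelets and PPIs but not anticoagulants (9.2.2). Lifting the exclusion alone would therefore not make this state verifiable.

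**The case against.** The strongest tempting reading is that the plan deletes a success route from uptake, so that every warfarin stopper is a lost success. With 3 to 5 stoppers added to the numerator, 30% would become (14.4 + 3)/51 = 34.1% to (13.8 + 5)/51 = 36.9%. The documents do not support this. The broad definition serves EHR accuracy only, and the uptake endpoint never counts a warfarin stop as success. Antiplatelet stopping by patients who stay on warfarin remains fully countable. A patient moved to another anticoagulant is still on combination therapy.

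A reader might also infer that the strategies drive warfarin stopping and so bias the arms. Section 7.1.1 aims them at antiplatelet stopping and PPI start, entry requires anticipated warfarin use of at least 90 days (6.2.1), and the Appendix 1 phrase is a note in certain rows of a table used to judge antiplatelet appropriateness. Such influence is possible but not shown.

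Three further defences have some force:

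- Section 4.1 already reports warfarin stops. That stands, but they are pooled with clinic closures and do not separate ended combination therapy from a switch of anticoagulant.
- The later exclusion was probably meant for stops before assessment #3. That is a fair reading of the intent, but the text runs to the end of the study and does not say so.
- Chart review cannot stand in for self-report in the accuracy endpoint. This stands in full, and the remedy has to respect it.

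**Conclusion.** The concern holds as an inconsistency between an exclusion rule, the stated analysis set and one endpoint definition. The early removal in 8.1.1 contradicts 11.2.1. The rule also takes randomized patients, including any who made a qualifying change, out of the uptake results, and its later part literally discards completed assessment #3 data. The mismatch in the definition of optimization is a smaller, separate point confined to EHR accuracy.

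The size is unknown because the documents give no warfarin-stop rate. With 3 to 5 stops among 51 patients, 30% uptake in the rest and no qualifying change among the stoppers (all assumed), uptake is 27% to 28%; it is higher if some of them made such a change. Importance is minor to moderate: the affected medication endpoints are exploratory and descriptive in a feasibility pilot. The denominator conflict reaches the primary and secondary endpoints and is the part most worth settling before analysis.

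**What to change.** 1. Reconcile 8.1.1 with 11.2.1 so that all randomized patients stay in the denominators, and state how a patient who was not called for assessment #1 is counted. A sensitivity result without early stoppers can be shown beside it.
2. Beside the interview-based uptake endpoint, add a chart-based analysis of all randomized patients. Show warfarin stoppers as a separate group in three categories: combination therapy ended; anticoagulant switched and combination therapy continues; not determinable.
3. Limit the assessment #3 exclusion to patients who stop warfarin or are closed to the clinic before that assessment is completed.
4. Align the EHR-accuracy definition in 4.1 with the effectiveness row (PPI start or stopping all antiplatelet therapy). Alternatively, keep it and record anticoagulant use at assessment #3, with a stated rule for patients who are not called.

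The cost is wording in 4.1, 8.1.1 and 11, and one chart-abstraction field for what may be a handful of patients. The alternative in item 4 adds one interview question. None of this changes care or the delivery of the strategies.
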